10.2.1 Cobomarsen Interruptions or Permanent Discontinuations

There are no dose reductions allowed for the cobomarsen infusion.

Infusion-related Adverse Events:

- If any grade 2 infusion-related AE(s) are observed/reported at any time during the infusion, the infusion rate should be decreased by one-half and supportive care medications/procedures should be initiated as appropriate. Upon resolution of the AE, the infusion rate should be increased to the rate used prior to the infusion-related AE. If the AE does not resolve prior to the completion of the infusion, the current infusion rate should be used with subsequent study treatment administration. Subjects who had grade 2 infusion-related reactions may receive premedication with subsequent infusions.
- If any grade 3 infusion-related AE(s) are observed/reported at any time during the infusion, the infusion should be temporarily interrupted, and supportive care medications/procedures should be initiated as appropriate. Once the symptoms decrease to baseline, the infusion may be resumed at one-half the rate and maintained at this rate for the remainder of the current infusion and subsequent infusions should be administered with premedication. If a grade 3 infusion-related reaction re-occurs, the subject should be permanently discontinued.
- If grade 4 infusion-related AE(s) are observed/reported at any time during the infusion, the infusion will be immediately discontinued, supportive care will be provided as needed, and no additional investigational product will be administered to the subject.

Specific Grade 2 Renal Adverse Events of interest and Grade 3 and 4 Adverse Events of Interest (Hematological, Hepatic, TSH, and Constitutional)

- **If any renal grade 2 AE(s) of interest** (e.g., creatinine elevation > 1.5 x baseline and above the ULN) a repeat serum creatinine level will be performed. If the repeat creatinine level is still > 1.5 x baseline and above the ULN, and no other cause is identified for this elevation, study drug will be interrupted until the level returns to baseline. Once the AE has decreased to baseline level, the infusion may be resumed. If the grade 2 AE re-occurs, the subject should be permanently discontinued.

- **If any grade 3 AE(s) of interest** are ongoing at the time of the planned infusion, the infusion should be delayed, and supportive care medications/procedures should be initiated as appropriate. Once the AE has decreased to baseline, the infusion may be resumed. If the grade 3 AE re-occurs, the subject should be permanently discontinued.
- **If a grade 4 AE is observed/reported** at any time and is felt to place the subject at life threatening risk, cobomarsen will be immediately discontinued, and the Medical Monitor should be contacted. No additional investigational product will be administered to that subject.

Other Grade 3 and 4 Adverse Events

- **If any clinically significant (symptomatic, requiring intervention) grade 3/4 AE(s)** or laboratory abnormalities are ongoing at the time of the planned infusion, the infusion should be delayed, and supportive care medications/procedures should be initiated as appropriate. Once the AE resolves or symptoms decrease to baseline, the infusion may be resumed. If the grade 3/4 AE re-occurs, the subject should be permanently discontinued.
- **If any non-clinically significant (asymptomatic, not requiring an intervention) grade 3/4 AE(s)** or laboratory abnormalities are observed/reported at any time, the infusion may be temporarily interrupted based on the investigator's opinion (in consultation with the Medical Monitor), and supportive care medications/procedures should be initiated as appropriate. Once the symptoms decrease to baseline, the infusion may be resumed.

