Abs Neutrophils	Calcium	Leukocytes		For WOCBP:
ANC	Chloride	Nitrite		Serum/urine pregnancy test
Basophils	Cholesterol	pH		
Eosinophils	CK ^b	Protein, Urine		
Hematocrit	C-Reactive Protein	Specific gravity		At Screening in the Randomized Period only:
Hemoglobin	Creatinine			HIV
Lymphocytes	Creatinine clearance (calculated)	Urine Chemistry		Hepatitis B
Mean Corpuscular Hemoglobin	Bilirubin (total and direct)	Myoglobin, Urine		Hepatitis C
Mean Corpuscular Hemoglobin Concentration	Glomerular Filtration Rate	Protein, Urine		
Mean Corpuscular Volume	GGT	Microalbuminuria		For confirmation of menopause only:
Mean Platelet Volume	GLDH ^c	Creatinine, Urine (Enzymatic)		FSH
Monocytes	Glucose	Protein/ Creatinine Ratio, Urine		
Neutrophils	LDH			
Platelets	Magnesium			
RBCs	Phosphorus			
WBCs	Potassium			
	Sodium			
	Total protein			
	Triglyceride			
	Urea (BUN)			
	Uric acid			

Abbreviations: Abs = Absolute; ALT = alanine aminotransferase; ANC = absolute neutrophil count; aPTT = activated partial thromboplastin time; AST = aspartate aminotransferase; BUN = blood urea nitrogen; CK = creatine kinase; GGT = gamma-glutamyl transferase; GLDH = glutamate dehydrogenase; FSH = follicle-stimulating hormone; HIV = human immunodeficiency virus; INR = international normalized ratio; LDH = lactate dehydrogenase; PT = prothrombin time; RBC = red blood cell; TSH = thyroids-stimulating hormone; WBC = white blood cell; WOCBP = women of childbearing potential

^a Hematology will include CBCs performed at the central lab and locally when performed concurrently with the flow cytometry

^b For grade 2 or 3 total CK: measure CK, CK isoenzymes weekly for 3 weeks and if total CK remains \leq the grade which triggered increased monitoring, continue to assess CK, CK isoenzymes along with regularly scheduled clinical chemistry assessments.

^c GLDH will be done as a reflex test if a grade 3 or 4 ALT or AST is observed.

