10.2.2 Vorinostat Dose Modifications, Interruptions, or Permanent Discontinuations

In general, doses of vorinostat should not be adjusted, reduced or interrupted for grade 1 AEs, but treatment may be instituted to control symptoms.

Vorinostat dose interruption or dose reduction may be considered if it is felt to be necessary (e.g., for AEs \geq grade 2) ([PDR 2018](#)).

- **Dose Reduction 1:** If vorinostat therapy intolerance occurs and dose reduction is deemed appropriate, the dose may be reduced to 300 mg orally once daily with food.
- **Dose Reduction 2:** If intolerance continues, the dose may be reduced to 300 mg once daily with food for 5 consecutive days each week.
- No re-escalation of vorinostat dose or schedule is allowed during the study.

Grade 3 and 4 Adverse Events

- **If any clinically significant (symptomatic, requiring intervention) grade 3/4 AE(s) or laboratory abnormalities** occur, the dose should be delayed, and supportive care medications/procedures should be initiated as appropriate. Once the AE resolves or symptoms decrease to baseline, vorinostat may be resumed. If the grade 3/4 AEs re-occurs, the subject should be permanently discontinued.
- **If any non-clinically significant (asymptomatic, not requiring an intervention) grade 3/4 AE(s) or laboratory abnormalities** are observed/reported at any time, vorinostat may be temporarily interrupted based on the investigator's opinion and supportive care medications/procedures should be initiated as appropriate. Once the symptoms decreased to baseline, vorinostat may be resumed.

QT/QTc Prolongation Adverse Events

Vorinostat is known to cause QT/QTc prolongation in patients. Please use the following criteria in the management of vorinostat patients on the clinical study.

- **If any clinically significant QT/QTc interval prolongation of ≤ 500 msec** is observed/reported at any time, vorinostat dosing should be interrupted and investigations about possible causes (electrolyte imbalance, concomitant medications, etc.), supportive care medications/procedures should be initiated. If other cause is found, once the QTc is documented to be back into normal range, a re-challenge with vorinostat could be considered, based on the investigator's discretion.

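### In the events-of-interest rules of Section 10.2.1, an asymptomatic event first seen at grade 4, needing no intervention and not felt life-threatening, gets a weaker dosing rule than the same event at grade 3

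*Combined protocol and SAP*

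**What the plan says.** Section 10.2.1 of the protocol has separate rules for three kinds of event under cobomarsen. Dose reduction is not allowed.

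- **Infusion-related events.** Action rises with grade: half the rate at grade 2, interruption at grade 3, and an immediate, permanent stop at grade 4 with no further condition.
- **Events of interest.** The block is headed "Specific Grade 2 Renal Adverse Events of interest and Grade 3 and 4 Adverse Events of Interest (Hematological, Hepatic, TSH, and Constitutional". If a grade 3 event of interest is present when an infusion is due, that infusion should be put off. Then: "Once the AE has decreased to baseline, the infusion may be resumed. If the grade 3 AE re-occurs, the subject should be permanently discontinued". No condition on symptoms is attached. The next bullet is the only one for grade 4. It acts if such an event is seen "and is felt to place the subject at life threatening risk, cobomarsen will be immediately discontinued, and the Medical Monitor should be contacted", and the subject then gets no more cobomarsen.
- **Other grade 3 and 4 events.** If symptomatic and requiring intervention, the infusion should be delayed, with a permanent stop on recurrence. If asymptomatic and not requiring intervention, "the infusion may be temporarily interrupted based on the" investigator's opinion, in consultation with the Medical Monitor. Restart follows: "Once the symptoms decrease to baseline, the infusion may be resumed". Nothing is said about recurrence.

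Section 10.3.6 lists the events of interest, among them neutropenia, lymphopenia, raised liver tests and raised TSH, and states that interruption rules specific to them exist.

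**The concern.** Dosing rules should not loosen as toxicity worsens. The infusion-related block escalates at every grade. The events-of-interest block does not: at grade 3 it asks for a hold and a stop on recurrence, and at grade 4 it acts only on a judgement that the event threatens life. Followed as written, a subject with the worse grade of a closely monitored toxicity could go on receiving weekly infusions where the milder grade would have led to a hold.

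The plan itself foresees such values. Table 5 in Section 7.2.2 has a footnote: "GLDH will be done as a reflex test if a grade 3 or 4 ALT or AST is observed". The block for other events expressly provides for asymptomatic grade 3/4 laboratory abnormalities. Scheduled samples are 4 weeks apart from Day 29 to Week 81 and 8 weeks apart after that, so a value could first be seen at grade 4. After 4 months some infusions may be given at home (Section 4.3.1), where a clear written rule helps.

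**Working it through.** **Rules side by side**, for an event of interest that has been recorded as an adverse event:

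| Case | Rule in its own block | If the block for other events also covers it |
|---|---|---|
| Grade 3, ongoing at a planned infusion | Should delay to baseline; permanent stop on recurrence | Specific rule taken to govern |
| Grade 4, felt life-threatening | Immediate permanent stop | Specific rule taken to govern |
| Grade 4, not felt life-threatening, symptomatic and requiring intervention | None | Should delay; permanent stop on recurrence |
| Grade 4, not felt life-threatening, asymptomatic, no intervention | None | May interrupt; no stop on recurrence |

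The protocol does not say whether the block for other events covers events of interest. On either answer, the last row is weaker than the first.

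**Is grade 4 life-threatening by definition?** Section 10.4.2 equates the two only for events not listed in CTCAE. For listed events, the grade 4 bullet adds its own condition, and the block for other events recognises grade 4 events that are asymptomatic. The definition does not close the gap.

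**How far the gap extends.**
- An event already held at grade 3 that worsens stays held, because the hold ends only at baseline.
- An event that falls from grade 4 to grade 3 and is ongoing at the next infusion meets the grade 3 rule.
- Under Section 10.5.1 a laboratory finding is an adverse event if the investigator judges it clinically significant. It also counts if it comes with clinically significant symptoms, prompts work-up or intervention, changes dosing or ends participation, or if the investigator otherwise considers it one. An asymptomatic value needing no intervention that is not so classed falls under laboratory abnormalities in the block for other events. It then gets the same optional hold at grade 3 and grade 4, with no inversion.

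**Schedule illustration.** Infusions of 282 mg are given on Days 1, 3, 5, 8 and weekly thereafter (Section 6.2.1). On-treatment hematology and chemistry are taken predose on Days 3, 8, 15 and 29, every 4 weeks from Week 9 to Week 81, then every 8 weeks (Sections 8.2.3 to 8.2.11). Count the infusions from one sample up to, but not including, the day of the next. The lower figure excludes the infusion on the first sample's own day (result known only afterwards); the higher figure includes it. Assume no optional hold and no unscheduled test.

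| Interval | Infusions | × 282 mg |
|---|---|---|
| Day 3 to 8 (Days 3, 5) | 1–2 | 282–564 |
| Day 8 to 15 (Day 8) | 0–1 | 0–282 |
| Day 15 to 29 (Days 15, 22) | 1–2 | 282–564 |
| Day 29 to Week 9, and each 4-week interval to Week 81 | 3–4 | 846–1,128 |
| Week 81 to 89, and each later 8-week interval | 7–8 | 1,974–2,256 |

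Under the grade 3 rule no infusion should be given while the event is ongoing. The rules apply to the 63 subjects planned for cobomarsen (Section 12.5.1) and to vorinostat subjects who cross over, whose infusion and laboratory days are the same (Section 9.2.2).

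**The case against.** The best reply is that no sensible site would dose through a grade 4 event it would have held at grade 3. The block's heading names both grades, so the grade 4 bullet reads naturally as a step above the grade 3 hold. The corner is also small. The event must be recorded as an adverse event, first seen at grade 4, asymptomatic, in need of no intervention, judged not life-threatening, and still grade 4 at the next infusion. Backstops exist: optional interruption in consultation with the Medical Monitor, discontinuation for unacceptable events (Section 5.4.1), extra laboratory tests at any time (Section 7.2.2), weekly review of adverse events (Section 8.2.9) and regular DMC safety review (Section 11.1).

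The narrowness stands, and it lowers the severity. The rest does not remove the point. The text does not say grade 3 or higher. For the individual subject the backstops rest on judgement, and DMC review is not a subject-level hold. The contrast should still not be drawn too sharply, because whether an asymptomatic grade 3 value counts as an adverse event is itself partly a matter of judgement.

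Three stronger readings are tempting and unsupported:
- *Section 10.2.1 as a whole acts at grade 4 only if life is threatened.* Infusion-related grade 4 events stop unconditionally, and symptomatic grade 3/4 events requiring intervention are delayed if the block for other events applies.
- *Every asymptomatic grade 3 laboratory value is held.* Only those recorded as adverse events are.
- *The infusion counts cap the excess exposure.* They end at the next sample, but nothing in the gap ends dosing there. A hold or an extra test would make them smaller.

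**Conclusion.** The point holds within the events-of-interest block: the stated rules give one kind of grade 4 event weaker protection than the same event at grade 3. It is a minor safety-rule correction. The conclusion assumes that the event is recorded as an adverse event and that, at grade 3, the specific rule governs over the block for other events.

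The documents give no basis for a frequency, and the infusion counts are illustrative schedule figures. A reader might infer a known toxicity problem, but the documents do not support that. Phase 1 reported no clinically significant renal, liver, coagulation, platelet or thyroid signal (Sections 2.1.3.2 and 2.3.1). It also gave no indication of an effect on general leukocyte populations, apart from an increase in NK cells at 900 mg (Section 2.1.3.2). The primary endpoint, alpha and power are not touched.

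**What to change.** In the delay-and-recurrence bullet for events of interest, replace grade 3 with grade 3 or 4 in both places: the trigger for delay and the trigger for permanent discontinuation on recurrence. Keep the next bullet, so that a grade 4 event felt to be life-threatening still means an immediate permanent stop.

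The cost is one bullet in the next amendment, a few more held infusions and perhaps a few more discontinuations. Section 10.2 makes more than 4 consecutive missed doses a reason to stop unless the investigator and Medical Monitor judge otherwise, so a slowly recovering value can still be handled case by case.

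Optional tidying, not part of this point: the block heading names renal events only at grade 2. The restart conditions for asymptomatic events in 10.2.1 ("Once the symptoms decrease to baseline, the infusion may be resumed") and 10.2.2 ("Once the symptoms decreased to baseline, vorinostat may be resumed") would also be better tied to the laboratory value where there are no symptoms.

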10.2.2 Vorinostat Dose Modifications, Interruptions, or Permanent Discontinuations

In general, doses of vorinostat should not be adjusted, reduced or interrupted for grade 1 AEs, but treatment may be instituted to control symptoms.

Vorinostat dose interruption or dose reduction may be considered if it is felt to be necessary (e.g., for AEs \geq grade 2) ([PDR 2018](#)).

- **Dose Reduction 1:** If vorinostat therapy intolerance occurs and dose reduction is deemed appropriate, the dose may be reduced to 300 mg orally once daily with food.
- **Dose Reduction 2:** If intolerance continues, the dose may be reduced to 300 mg once daily with food for 5 consecutive days each week.
- No re-escalation of vorinostat dose or schedule is allowed during the study.

Grade 3 and 4 Adverse Events

- **If any clinically significant (symptomatic, requiring intervention) grade 3/4 AE(s) or laboratory abnormalities** occur, the dose should be delayed, and supportive care medications/procedures should be initiated as appropriate. Once the AE resolves or symptoms decrease to baseline, vorinostat may be resumed. If the grade 3/4 AEs re-occurs, the subject should be permanently discontinued.
- **If any non-clinically significant (asymptomatic, not requiring an intervention) grade 3/4 AE(s) or laboratory abnormalities** are observed/reported at any time, vorinostat may be temporarily interrupted based on the investigator's opinion and supportive care medications/procedures should be initiated as appropriate. Once the symptoms decreased to baseline, vorinostat may be resumed.

QT/QTc Prolongation Adverse Events

Vorinostat is known to cause QT/QTc prolongation in patients. Please use the following criteria in the management of vorinostat patients on the clinical study.

- **If any clinically significant QT/QTc interval prolongation of ≤ 500 msec** is observed/reported at any time, vorinostat dosing should be interrupted and investigations about possible causes (electrolyte imbalance, concomitant medications, etc.), supportive care medications/procedures should be initiated. If other cause is found, once the QTc is documented to be back into normal range, a re-challenge with vorinostat could be considered, based on the investigator's discretion.
- **If any QT/QTc interval prolongation of > 500 msec** is observed, vorinostat should be permanently discontinued. Consultation with a cardiologist is required and the subject should have continuous ECG monitoring until released by the cardiologist.

If vorinostat is not tolerable and therapy must be discontinued, study assessments will be continued on an every-4-week visit schedule to follow the subject until confirmed progression, if the subject consents to continued follow-up visits.

Whenever possible, additional therapies for MF should not be initiated until disease progression is documented. Subjects will not be eligible for the crossover period of the study unless:

- Skin disease progression is confirmed;
- No additional systemic therapies for MF have been initiated.

10.3 Definition of Adverse Events

10.3.1 Adverse Event

An AE is any untoward medical occurrence whether or not considered drug related. An AE can be any unfavorable and unintended sign (e.g., an abnormal laboratory finding), symptom, or disease temporally associated with the use of a drug and does not imply any judgment about causality. An AE can arise with any use of the drug (e.g., off-label use, use in combination with another drug) and with any route of administration, formulation, or dose, including an overdose.

Please note that disease progression is not considered an AE. However, a primary adverse event associated with disease progression that meets the criteria for an SAE should be reported.

10.3.2 Suspected Adverse Reaction

A suspected adverse reaction is any AE for which there is a reasonable possibility that the drug caused the AE. For the purposes of Investigational New Drug (IND) safety reporting, “reasonable possibility” means there is evidence to suggest a causal relationship between the drug and the AE. Suspected adverse reaction implies a lesser degree of certainty about causality than adverse reaction, which means any AE caused by a drug.

10.3.3 Life-Threatening Adverse Event or Life-Threatening Suspected Adverse Reaction

An AE or suspected adverse reaction is considered “life-threatening” if, in the view of either the Investigator or Sponsor, its occurrence places the subject at immediate risk of death. It does not include an AE or suspected adverse reaction that, had it occurred in a more severe form, might have caused death.

10.3.4 Serious Adverse Event or Serious Suspected Adverse Reaction

An AE or suspected adverse reaction is considered “serious” if, in the view of either the Investigator or Sponsor, it results in any of the following outcomes:

- Death;
- A life-threatening AE (see [Section 10.3.3](#));
- Requires inpatient hospitalization or prolongation of existing hospitalization;
- A persistent or significant disability or incapacity or substantial disruption of the ability to conduct normal life functions;

- A congenital anomaly/birth defect;
- Important medical events that may not result in death, be life-threatening, or require hospitalization may be considered serious when, based upon appropriate medical judgment, they may jeopardize the subject and may require medical or surgical intervention to prevent one of the outcomes listed in this definition. Examples of such medical events include allergic bronchospasm requiring intensive treatment in an emergency room or at home, blood dyscrasias or convulsions that do not result in inpatient hospitalization.

10.3.5 Unexpected Adverse Event or Unexpected Suspected Adverse Reaction

An AE or suspected adverse reaction is considered “unexpected”:

- If it is not listed in the Investigator’s Brochure or is not listed at the specificity or severity that has been observed, or
- If it is not consistent with the risk information described in the general investigational plan, or elsewhere in the current application, as amended.

For example, under this definition, hepatic necrosis would be unexpected (by virtue of greater severity) if the Investigator’s Brochure referred only to elevated hepatic enzymes or hepatitis. Similarly, cerebral thromboembolism and cerebral vasculitis would be unexpected (by virtue of greater specificity) if the Investigator’s Brochure listed only cerebral vascular accidents.

“Unexpected,” as used in this definition, also refers to AEs or suspected adverse reactions that are mentioned in the Investigator’s Brochure as occurring with a class of drugs or as anticipated from the pharmacological properties of the drug but are not specifically mentioned as occurring with the particular drug under investigation.

